For the CGI-I Symptoms Overall domain at Week 12, the Mixed Model Repeated Measures (MMRM) analysis showed a significant improvement for OV101 compared to placebo for the OV101 groups combined ($P=0.0103$) and for the OV101 QD group ($P=0.0006$). At Week 12, subjects in the OV101 QD group showed significant improvement in CGI-I Symptoms Overall regardless of age.

For the CGI-I Sleep domain at Week 12, the MMRM analysis showed a significant improvement for OV101 compared to placebo for the OV101 groups combined ($P=0.0236$) and for the OV101 QD group ($P=0.0141$).

In post hoc analyses at Week 12, most subjects in the OV101 groups combined (54.5%) had responses of minimally improved (34.5%) or much improved (20.0%) for CGI-I Symptoms

Overall, compared to 22.2% of subjects in the placebo group (14.8% minimally and 7.4% much improved). The percentages of subjects with improvement were larger in the OV101 QD group (66.6%; 29.6% minimally, 37.0% much improved) than in the OV101 BID group (42.8%; 32.1% minimally, 10.7% much improved).

NEPTUNE (OV101-19-001) will be a multicenter, randomized, placebo-controlled, parallel-group study to evaluate the efficacy and safety of OV101 in pediatric subjects with AS. Subjects who complete the study will be eligible to enroll in the ongoing OV101-18-002 (ELARA) open-label extension study, provided they meet the eligibility criteria for ELARA.

2 Study Objectives

All efficacy study objectives will be assessed in the pediatric AS study population of subjects who are 4 to 12 years old. All safety study objectives will be assessed in the pediatric AS study population of subjects who are 2 to 12 years old.

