7. Has enrolled in any other interventional clinical study or used any investigational agent or device, or has participated in any investigational procedure, within the 30 days before screening or does so concurrently with this study.
8. Is allergic to OV101 or any excipients of study drug.
9. The subject or LAR/caregiver is unable to comply with study requirements (based on investigator assessment).
10. Is a family member of the investigator and/or study site staff.

[figure not shown]
Study Design:

The study will comprise a screening period within the 28 days preceding Day 1; a visit on Day 1 for baseline assessments, the first dose of study drug, and sparse sampling of blood; subsequent doses of study drug taken each evening approximately 30 minutes before bedtime for 12 weeks starting on Day 2; and study site visits for efficacy and safety assessments over a 12-week treatment period. After the baseline visit, the study site visits will occur at Week 6 and Week 12 (end of treatment [EOT]). Phone safety visits will occur during up-titration of the study drug (Day 6 and Day 11). Unless a subject decides to participate in the ELARA open-label extension study, an end of study (EOS) phone safety visit will occur approximately 2 weeks after the last dose of study drug to assess safety and tolerability associated with discontinuation of treatment. Subjects eligible for and willing to enroll in the ELARA study will have the NEPTUNE EOT visit be their NEPTUNE EOS visit, and their NEPTUNE EOT visit will serve as their ELARA baseline visit. A subject will be considered to have completed the NEPTUNE study after completing the EOS visit. The total duration of the study for a subject will be approximately 18 weeks.

Random assignment of subjects for efficacy assessment (to either OV101 or placebo treatment in a 1:1 ratio) will be stratified by subject age at screening and by region, with a maximum of 12 subjects per study site (unless authorized by Sponsor). The randomization strata for age at screening will be 9 to 12 years old (inclusive) and 4 to 8 years old (inclusive), with at least 24 subjects per age category. The randomization strata for region will be US and outside US. Approximately 5 subjects 2 to 3 years old (inclusive) will be enrolled for safety [REDACTED] assessments only and will be assigned to treatment with OV101. Within each age group, dosing will be assigned based on body weight at screening.

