For each subject, after informed consent is obtained, screening assessments will be completed within the 28 days preceding Day 1 (baseline). On Day 1, each subject who meets all eligibility criteria will receive the first assigned blister cards of study drug capsules according to the treatment code (except for subjects 2 to 3 years old, who will receive study drug capsules in bottles), sufficient to last until the Week 6 visit, when blister cards (or bottles for ages 2 to 3 years) will be collected and unused study drug will be counted. Study drug will be similarly dispensed at the Week 6 visit, and blister cards (or bottles for ages 2 to 3 years) will be collected and unused study drug will be counted at the Week 12 visit. Caregivers/LARs will be provided an additional blister card in case of unexpected delays for study visits (e.g., inclement weather/flight delays).

The LAR/caregivers will complete paper seizure diaries on behalf of subjects throughout the study, from issuance during screening (and at study visits) through Week 12 (EOT).

Safety information will be collected during phone calls on Day 6 and Day 11 and during the EOS visit, as well as during every study site visit. Each subject's LAR/caregiver will be instructed to contact the study center if the subject experiences any adverse events (AEs), is unable to take the study drug as prescribed, [REDACTED]

At the investigator's discretion throughout the study, subjects may be evaluated at unscheduled clinic visits for reasons related to subject safety. At unscheduled visits, subjects will be queried about AEs and changes in concomitant medications and evaluated for suicidality. Safety laboratory assessments may be conducted. Periodic interim review of safety data will be performed by the IDMC and as part of routine pharmacovigilance activities.

Estimated Study Duration:

[figure not shown]
After informed consent is obtained, screening assessments will be conducted within the 4 weeks preceding baseline, followed immediately by treatment for 12 weeks and a 2-week follow-up period (for subjects not enrolling into the ELARA study), for a maximum duration of individual subject participation of 18 weeks. Four study site visits are scheduled for each subject.

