6.4.2.2 Seizure Diary

The seizure diary is a caregiver-reported clinical outcome assessment measure that captures the total number and duration of seizures. Caregivers will record the number, duration, and type of seizures each day using the paper seizure diary. Also, refer to Section 6.4.1.1 for AE reporting criteria for these seizure events.

The caregiver will be trained by the site with specific instructions beginning with the screening visit to ensure compliance in recording seizures. The seizure diary will be completed each day during 12 weeks of treatment beginning at screening and continuing through the EOT. Seizure diaries will be collected and reviewed by the investigator with the subject's caregiver for proper recording at the baseline, Week 6, and Week 12 (or EOT) study site visits. Seizure Identification Form and Diagnostic Review Forms (SIF/DRF) will be completed by site personnel for every eligible subject. This information will be faxed or emailed to The Epilepsy Study Consortium (TESC) for review and approval. The SIF/DRF will be used to ensure that the seizures are

classified accurately. SIF and DRF forms will be collected for patients who have enrolled/completed the study if feasible.

For the prospective baseline period, the seizure frequency (expressed as a 28-day frequency) will be calculated as

$$(\# \text{ of seizures}) / (\# \text{ of days seizures were assessed}) \times 28$$

Seizure frequency calculated through this method will be used to confirm the eligibility.

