7.2.2 Safety Endpoints

- Incidence of AEs
- Change in clinical laboratory parameters from baseline to each post baseline assessment
- Shift in clinical laboratory parameters from baseline to each post baseline assessment
- Change in vital sign measurements from baseline to each post baseline assessment
- Shift in physical examination parameters from baseline to each post baseline assessment
- Change in suicidality assessment (ABC-I) from baseline to each postbaseline as assessed by ABC-I. The ABC-I will serve as a surrogate measure for suicidality
- Percent change in seizure frequency (expressed as a 28-day frequency) from baseline to each post baseline timepoint

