- **For subjects 2-3 years old**

- Screening shall be performed on-site. If pandemic restrictions preclude on-site visits, then screening of subjects 2-3 yrs old shall be placed on a temporary hold until permissible under local and investigative site's guidelines
- Informed Consent may be sent to the subject either electronically (pdf format) or by mail prior to the scheduled screening visit. The signed consent should be returned by the subject to the site and appropriately filed. If Informed Consent is completed remotely, a wet ink signature on ICF should be returned to the site via courier.

Guidance for subjects scheduled for Randomization/Baseline Visit

[figure not shown]
- Randomization visits can only occur when patients can physically be present on-site
- If the baseline visit cannot be conducted within 28 days of screening, it should be captured as a protocol deviation due to pandemic restrictions but do not automatically screen fail the subject. IWRS and EDC will not automatically screen fail subjects in this case
- Every attempt should be made to follow procedures at the randomization visit as per study protocol. Any deviation should be appropriately documented and reported to each site's IRBs/ECs per their reporting guidelines
- Additional instructions pertaining to the randomization visit will be provided for subjects who are still in the screening phase when pandemic restrictions are scaled back, and subjects are able to attend clinic visits in person

- Seizure [redacted] diaries must be collected and reviewed as per protocol procedures and Epilepsy Consortium instructions including SIF and DRF forms. Physical/electronic PDF copies of diaries (including medication diary) should be provided in preparation of week 6 and week 12 visits
- Preprinted shipment labels and envelopes should be provided to caregivers to receive diaries
- Upon retrieval of diaries, EDC should be updated accordingly

Guidance for established subjects completing Week 6 Study Visit

- Schedule the visit as close as possible to Week 6 date to allow time to ship IP.
- When on-site visits are not feasible, remote assessment of the CGI-I-AS, CGI-S-AS, VABS3, and other PROs) may be performed via your institution-approved (HIPAA compliant) telehealth system. Telehealth assessments must be consistent with local policies and standards. The requirements for data protection of Personal Health Information (PHI) must be adhered to.

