3.9.6 Seizure Diary Data

The number of subjects reporting a new type of seizure during treatment and the type of new seizures reported during treatment will be summarized. Additionally, the seizure frequency per 28 days (normalized) will be calculated for the following study periods: Baseline (Screening to Day -1), Week 6 (Day 1 to Week 6 visit date or EOT before Day 43), and Week 12 (Week 6 visit date + 1 day to Week 12 visit date or EOT between Day 44 and Day 85). Percent change in seizure frequency per 28 days from Baseline to all post-baseline study visits also will be summarized descriptively by treatment group.

All seizure diary results will be included in a subject listing.

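### Per-child percent change in 28-day seizure frequency is biased when baseline counts are small; a pooled rate per assessed diary day should be the main by-arm display

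*Protocol*

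**What the plan says.** The Synopsis (Study Design) and Protocol 3.1 bound screening from above only: "The study will comprise a screening period within the 28 days preceding Day 1". The Pandemic Addendum (Protocol 13) lets it run longer: "If the baseline visit cannot be conducted within 28 days of screening, it should be captured as a protocol deviation".

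Protocol 6.4.2.2 ties the seizure baseline to screening: "The seizure diary will be completed each day during 12 weeks of treatment beginning at screening and continuing through the EOT". The same section introduces the scaling with "For the prospective baseline period, the seizure frequency (expressed as a 28-day frequency) will be calculated as", followed by a formula that divides the number of seizures by the number of days assessed and multiplies by 28.

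The safety endpoint in Protocol 7.2.2 is "Percent change in seizure frequency (expressed as a 28-day frequency) from baseline to each post baseline timepoint". SAP 3.9.6 implements it: "the seizure frequency per 28 days (normalized) will be calculated for the following study periods: Baseline (Screening to Day -1"), then a Week 6 and a Week 12 period, with percent change summarised descriptively by arm. SAP 4.2.1 computes percent change by dividing by the baseline value.

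No readable section gives a minimum number of baseline diary days or says what happens when the baseline is zero. The schedule of activities (Protocol Table 6–1, SAP Table 1) and the study manual were not in the text reviewed and could contain a minimum.

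**The concern.** Percent change cannot be computed for a child with no baseline seizures. If seizures are infrequent, or the baseline is short, many children fall in that group. Those who remain are the ones who happened to have a seizure in the window, and scaling makes that one event large: 1 seizure in 7 days becomes 4 per 28 days, against 1 per 28 days over a full window. Follow-up of about 6 weeks per period then drifts back towards the true rate, and the child appears to improve whatever the drug does.

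The by-arm figure therefore depends on the seizure rate and on how long screening lasted, as well as on any treatment effect. Children who have no baseline seizures and start having them on treatment do not enter the percent-change summary at all.

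Seizure diary data are named in the safety objective. The Protocol Introduction lists seizure among the events that were more frequent on OV101 than on placebo in the Phase 2 study. Exclusion criterion 2 removes poorly controlled seizures, so low baseline rates are plausible here.

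**Working it through.** The documents give no seizure rate, screening-length distribution or target figure for this endpoint, so there is nothing of the plan's own to reproduce. The check applies the plan's formulas to assumed scenarios.

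**Inputs from the documents.** Scaled frequency = count / days × 28 (Protocol 6.4.2.2). Percent change = (post − baseline) / baseline × 100 (SAP 4.2.1). Screening is at most 28 days outside the pandemic exception. Exclusion 2b removes more than 3 short seizures a week, so roughly 3 × 4 = 12 per 28 days is the most it admits.

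**Assumptions.** Poisson counts; true baseline rate λ of 0.5 to 12 per 28 days; baseline length d of 7 to 28 days; on-treatment rate r × λ. A 42-day follow-up period is used for medians and simulations; the mean does not depend on it.

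**Formula.** The expected baseline count is m = λd/28, with X ~ Poisson(m). Among children with X ≥ 1:

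mean percent change = 100 × (r × m × E[1/X | X ≥ 1] − 1)

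The result depends on λ and d only through m.

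**Worked case.** λ = 2 and d = 7 give m = 0.5. The chance of a non-zero baseline is 1 − e^(−0.5) = 0.39, and E[1/X | X ≥ 1] = 0.879. With r = 1.5: 1.5 × 0.5 × 0.879 − 1 = −0.34. The mean scaled baseline among children kept is 2 / 0.39 = 5.1 per 28 days, against a true 2.

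| m | Example (λ per 28 days, baseline) | Children kept | No change | 50% rise | Doubling |
|---|---|---|---|---|---|
| 0.25 | 1, 7 days | 22% | -77% | -65% | -53% |
| 0.5 | 2, 7 days; 1, 14 days; 0.5, 28 days | 39% | -56% | -34% | -12% |
| 1 | 4, 7 days; 1, 28 days | 63% | -23% | +15% | +53% |
| 2 | 8, 7 days; 2, 28 days | 86% | +15% | +73% | +131% |
| 3 | 12, 7 days | 95% | +30% | +95% | +160% |
| 12 | 12, 28 days | about 100% | +10% | +65% | +121% |

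**Baselines spread evenly over 7 to 28 days**, averaged over children with a non-zero baseline:

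| λ per 28 days | No change | 50% rise | Doubling |
|---|---|---|---|
| 1 | -44% | -15% | +13% |
| 2 | -10% | +35% | +81% |
| 4 | +19% | +79% | +139% |

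**Median.** At λ = 2 with a 50% rise, the median is -33% for a 7-day baseline (77% of evaluable children read as a fall) and +33% for 28 days (31% read as a fall). The median does not rescue the display.

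**Children with different rates.** With exponentially distributed rates (mean 2 per 28 days, capped at 12) and a 50% rise, a 7-day baseline gives mean -10% and median -30%; 28 days gives +55% and +33%.

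**Arm contrast, 50% rise against no change (true difference 50 points).** It equals 50 × m × E[1/X | X ≥ 1]. At λ = 2 this is 50 × 0.439 = 22 points with 7 days and 50 × 1.153 = 58 points with 28 days.

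**Pooled rate.** Simulating 45 children at a mean of 2 per 28 days, baselines of 7 to 28 days and 42 days of follow-up, total seizures over total days gives about +2% to +3%, +53% to +54% and +103% to +105% for true ratios of 1, 1.5 and 2. The result is similar whether children share one rate or differ.

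**The case against.** A reader might infer that short baselines generally make a real rise look like a fall. The documents do not support that. The reversal needs a small expected count. With a 7-day baseline a 50% rise already reads +15% at 4 per 28 days and +95% at 12, and with baselines spread over 7 to 28 days it reads +35% at 2. Neither the actual rates nor the actual screening lengths are given. That objection stands, and it limits the claim.

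A second tempting reading is that the missing minimum is the cause. It is not. Count over days is an unbiased rate; the bias comes from sparse counts together with the loss of zero baselines. At 0.5 per 28 days a full 28-day baseline still turns a 50% rise into -34%. A 14-day minimum gives the same -34% at 1 per 28 days when every baseline is exactly 14 days, and -6% when baselines run evenly from 14 to 28 days. Baselines longer than 28 days under the pandemic exception increase the expected count and so ease the sparse-count problem.

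Third, a reader might infer that harm on OV101 would be hidden. Baseline precedes treatment and both randomized arms are distorted alike, so the contrast is diluted, not reversed. Seizure safety also has other outputs. Protocol 6.4.1.1 makes a clear increase, a new seizure type or status epilepticus an adverse event; SAP 3.9.1.6 tabulates seizure events of special interest by arm; SAP 3.9.6 counts new seizure types and lists all diary data; Protocol 7.9.5 summarises diary data at each visit. The IDMC includes a pediatric epileptologist and may see unblinded data.

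These are real safeguards, but they do not repair the named endpoint. The clear-increase rule is itself judged against the child's baseline, and the new-type count does not register more frequent seizures of an existing type.

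**Conclusion.** The point holds in limited form. Per-child percent change from a scaled baseline is an unreliable by-arm summary here because the same true change reads differently according to seizure rate and screening length. When the expected baseline count is below about 1, it is biased downward, and at about 0.5 a true 50% rise reads -34%. At higher counts the mean is often overstated instead (+73% at an expected count of 2). In the case computed, the arm contrast for a 50% rise shrinks to 22 points with a 7-day baseline, against 58 with 28 days and a true 50.

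The sizes rest on Poisson counts and assumed rates and baseline lengths, so they are scenarios and not predictions for this trial. A minimum diary length in the unseen schedule or manual would narrow the range but not remove the bias. The endpoint is descriptive and other seizure outputs exist, so this does not threaten the trial's conclusions. It is worth correcting because it concerns a named safety objective and the correction is cheap.

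**What to change.** In SAP 3.9.6, before unblinding:

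- Make the main by-arm display the pooled rate for each period: total seizures / total assessed diary days × 28. Include children with zero baseline seizures.
- Add the OV101:placebo rate ratio with 95% CI from a count model with log assessed days as offset (for example negative binomial, to allow for differences between children), labelled descriptive and supportive.
- Tabulate assessed baseline diary days by arm.
- Keep per-child percent change as a secondary display, and show the number of children excluded for a zero baseline in each arm.
- A minimum number of assessed baseline days for that secondary display is optional. If the schedule or study manual already sets one, cite it. It does not cure the bias alone.

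The cost is SAP wording, one extra table and one simple model on data already collected; no study procedure changes. The drawback is that a pooled rate gives more weight to children with many seizures, which is a reason to keep the per-child display beside it.

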2.1 Primary Objective

- To evaluate the efficacy of OV101 versus placebo as assessed by the Clinical Global Impressions-Improvement-Angelman syndrome (CGI-I-AS) score at Week 12.

2.2 Secondary Objectives

[figure not shown]
Key Secondary Objectives:

The purpose of the key secondary objectives is to fulfil a recommendation of the EMA for a responder analysis.

- To evaluate the efficacy of OV101 vs placebo as assessed by the proportion of subjects who experience any meaningful improvement on study treatment (defined as CGI-I-AS score of 1, 2, or 3 at Week 12)
- To evaluate the efficacy of OV101 vs placebo as assessed by the proportion of subjects who experience a response of much improved or very much improved (defined as CGI-I-AS score of 1 or 2 at Week 12)

Other Secondary Efficacy Objectives:

- 
- To evaluate the efficacy of OV101 versus placebo on Communications, Socialization, Daily Living Skills, Motor Skills, and Maladaptive Behavior domains assessed by the Vineland Adaptive Behavior Scale, 3rd Edition (VABS-3).
 - To evaluate the efficacy of OV101 versus placebo based on the Clinical Global Impressions-Severity-Angelman syndrome (CGI-S-AS) Symptoms Overall score.
 - To evaluate the relationships of CGI-S-AS Symptoms Overall and CGI-S-AS domains at baseline with CGI-I-AS at Week 12.

2.5 Safety Objectives

The safety objectives of this study are to evaluate the safety and tolerability of OV101 in subjects 2 to 12 years old, including seizure diary data and assessment of suicidality.

3 Investigational Plan

3.1 Study Design

[figure not shown]
This will be a Phase 3, randomized, double-blind, placebo-controlled, parallel-group study, conducted in clinic settings, to evaluate the efficacy and safety of OV101 in pediatric subjects with AS. Male and female subjects with a previous diagnosis of AS (with molecular confirmation) will be eligible for inclusion (Section 4.1). The study will comprise a screening period within the 28 days preceding Day 1; a visit on Day 1 for baseline assessments, the first dose of study drug, and sparse sampling of blood; subsequent doses of study drug taken each evening approximately 30 minutes before bedtime for 12 weeks starting on Day 2; and study site visits for efficacy and safety assessments over a 12-week treatment period. After the baseline visit, the study site visits will occur at Week 6 and Week 12 (end of treatment [EOT]). Phone safety visits will occur during up-titration of the study drug (Day 6 and Day 11). Unless a subject decides to participate in the ELARA open-label extension study, an end of study (EOS) phone safety visit will occur approximately 2 weeks after the last dose of study drug to assess safety and tolerability associated with discontinuation of treatment. Subjects eligible for and willing to enroll in the ELARA study will have the NEPTUNE EOT visit be their NEPTUNE EOS visit, and their NEPTUNE EOT visit will serve as their ELARA baseline visit. A subject will be considered to have completed the NEPTUNE study after completing the EOS visit. For NEPTUNE subjects participating in ELARA, the EOS visit that occurs approximately 2 weeks after the EOT will take place in the ELARA study only. The total duration of the study for a subject will be approximately 18 weeks. The schedule of activities for this study is fully presented in Table 6–1.

[figure not shown]
Approximately 95 subjects will be enrolled in the study at approximately 15 study sites in the United States, Israel, Australia and/or Europe. Approximately 90 subjects 4 to 12 years old (inclusive) will be enrolled for both efficacy and safety assessments, and not more than 12 of these subjects will be enrolled at a study site (unless authorized by Sponsor). Random assignment of subjects for efficacy assessment (to either OV101 or placebo treatment in a 1:1 ratio) will be stratified by age at screening [9 to 12 years old (inclusive) and 4 to 8 years old (inclusive)] and by region (US and outside US). There will be at least 24 subjects per age group. Approximately 5 subjects 2 to 3 years old (inclusive) will be enrolled for safety [REDACTED] assessments only and will be assigned to treatment with OV101. Within each age group, dosing will be assigned based on body weight (Table 5–1).

[figure not shown]
For each subject, after informed consent is obtained (Section 9.3), screening assessments will be completed within the 28 days preceding Day 1 (baseline). On Day 1, eligible subjects will receive study drug capsules according to treatment code (sufficient to last until the Week 6 visit).

Caregivers/LARs will be provided an additional blister card in case of unexpected delays for study visits (e.g., inclement weather/flight delays). Study drug will be similarly dispensed at the Week 6 visit. Unused study drug will be collected and counted at Week 6 and 12.

